## 4.0 TREATMENT PLAN

### 4.1 Schema for LCCC 1626

Talimogene laherparepvec (TVEC) will be given intrapleural (IP) instillation for up to 9 cycles (includes seroconversion dose 4ml of 10^6 pfu/mL) in Dose Level cohorts 1 and 2. Nivolumab (240 mg IV) will be co-administered with talimogene laherparepvec (4ml of 10^8 pfu/mL) for up to 9 cycles in the Dose Level 2 cohort, with 3 week interval between cycle 1 and cycle 2 to allow for seroconversion. Patients will be allowed to continue nivolumab monotherapy per standard of care (240 mg IV Q2W) as long as they are responding to therapy (i.e., until disease progression, untoward toxicity, or withdrawal for other reasons).

This Phase Ib/II trial includes a safety run-in period using 3 + 3 dose escalation rules to evaluate the feasibility of administering talimogene laherparepvec into the intrapleural space of patients with MPE via a pleurX catheter. All infusions of talimogene laherparepvec will occur in 200cc normal saline (NS) followed by 20cc of sterile saline to clear the catheter, regardless of dose. Subjects will be instructed to avoid drainage for at least 24 hours, then to drain the catheter (and flush with 20 cc of sterile saline) when next needed to palliate shortness of breath, consistent with standard of care use of the pleurX catheter. If a patient becomes dyspneic <24 hours after talimogene laherparepvec administration, they should consult the interventional pulmonology team at UNC to determine if catheter drainage is necessary. Patients who experience severe shortness of breath <24 hours after

intrapleural talimogene laherparepvec will be allowed to have their catheter drained.

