## 2.4 Study Endpoints

### 2.4.1 Primary Endpoint

**2.4.1.1 Phase I:** Clinician assessed toxicity will be classified and graded according to the National Cancer Institute's Common Terminology Criteria for Adverse Events (NCI-CTCAE, version 5.0).

**2.4.1.2 Phase II: Resolution ( $\leq 50$ cc drainage over three consecutive every other day drainages) of pleural fluid accumulation accompanied by patient-defined improvement in symptoms (dyspnea, cough and/or chest pain).**

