In Dose Level 2 (expected Phase II dose), the first 3 patients will receive both IP talimogene laherparepvec and IV nivolumab. The first dose of talimogene laherparepvec will be administered on Cycle 1, Day 1 at 4mL of  $10^6$  pfu/mL in 200 cc normal saline (IP) to seroconvert HSV-seronegative patients. Three weeks will be given for seroconversion. Subsequent doses of talimogene laherparepvec at 4ml of  $10^8$  pfu/mL + Nivolumab 240 mg IV will be administered every two weeks starting on Cycle 2, Day 1 for up to 8 cycles of therapy. Patients will be assessed for DLTs related to IP administration of talimogene laherparepvec after seroconversion and 2 cycles of combination therapy (i.e., 7 weeks of study treatment). If  $\geq 2$  patients experience DLT, the study will be discontinued. If 1 patient out of 3 has DLT, 3 additional patients will be recruited and treated at the same dose level. If 0 out of 3 or  $\leq 1$  patient out of 6 has a DLT in the dose level 2 cohort, the study will recruit additional patients in Phase II at this dose level and accrue a total of 24 patients as per study goal. All patients treated at dose level 2 in Phase I or Phase II, will be included in analyses of safety and efficacy. Safety stopping rules will ensure the safety of subjects receiving combination treatment in Phase II (see [Statistical Considerations in section 9.0.](#))

Subjects may continue talimogene laherparepvec for up to 9 cycles (i.e. alone or with nivolumab) until resolution of pleural effusion or they experience systemic disease progression. Subjects who have resolution of pleural effusion as defined by

the primary endpoints may continue nivolumab monotherapy per standard of care until disease progression (see section 4.2 for details on treatment and section 6.5.2).

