##### **Standard Drainage -**

Drainage will take place either in the subject's home or in a suitable clinical area. All drainages after placement should be performed using standard aseptic technique and, unless connected to an inpatient drainage device, should be performed using PleuX vacuum drainage bottles. All drainage volumes should be recorded in the subject's diary. The subject must contact the clinical site once he/she has drained <50mL on 3 consecutive drainages performed every other day.

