##### **Study Drug Drainage -**

Following IP infusion of TVEC via the TPC, patients will allow the product to dwell for 24 hours. After 24 hours the patients will drain their TPC either fully or up to the point of symptom development (chest pain/pressure, progressive dyspnea, intractable coughing). Following drainage of the dwelled product, the patients will follow an every other day (QOD) drainage schedule. Patients will drain as fully as possible, stopping at the point of symptom development.

In the event patients develop dyspnea after IP infusion of TVEC they will be allowed to drain their TPC earlier than 24 hours.

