All IP infusions of talimogene laherparepvec will be in 200cc NS followed by 20cc of sterile saline to flush the catheter. Subjects will be instructed to allow the product to dwell for at least 24 hours after which they should next drain the catheter when next needed to palliate shortness of breath, consistent with standard of care use of the catheter. Subjects or their caregivers will be instructed to use medical gloves when draining the catheter and to avoid physical contact with fluid drained from the catheter. Standard drainage bottles will be used. Subjects will be allowed to either add bleach to the bottle then dispose per standard procedures or return to the investigators for disposal. These precautions will be advised permanently after study initiation (See [Appendix D](#) -Information Sheet for Caregivers, Family Members or other Close Contacts to Clinical Trial Participants being given Talimogene Laherparepvec).

Nivolumab 240 mg will be administered (per standard of care) as a 30-minute IV infusion on D1 of each cycle every two weeks.

Nivolumab and talimogene laherparepvec may be administered in either order. Administration of the two agents should be within 30 hours of each other.

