## 11.5 Appendix E: Patient Catheter Drainage Diary

### **PleuRx® Drainage Schedule & Patient Instructions**

Please drain fluid through the catheter every other day using a one liter bottle. You should drain fluid until there is no more fluid coming out or you develop chest pain or persistent cough. You should drain no more than 1 liter (1000 cc) of fluid every other day.

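### Sections 4.1, 4.2 and 5.1.3 let shortness of breath trigger the first drainage after a dose, whereas Section 4.1.2 sets it after 24 hours and then every other day, the schedule the Phase II endpoint needs.

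*Combined protocol and SAP*

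**What the plan says.** Two instructions cover the first drainage after an intrapleural dose.

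- **Symptom trigger.** Section 4.1 sets a minimum of 24 hours without drainage; subjects are "then to drain the catheter (and flush with 20 cc of sterile saline) when next needed to palliate shortness of breath". Section 4.2 repeats this: after the dwell "they should next drain the catheter when next needed to palliate shortness of breath". Section 5.1.3 uses the same words.
- **Fixed time.** Section 4.1.2 opens by presenting itself as the way catheter drainage will be done in both phases. Under Study Drug Drainage it says: "After 24 hours the patients will drain their TPC either fully or up to the point of symptom development". It continues: "Following drainage of the dwelled product, the patients will follow an every other day (QOD) drainage schedule".

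Three other places assume the fixed schedule. The Phase II primary endpoint (2.4.1.2) needs at most 50 cc "drainage over three consecutive every other day drainages", together with symptom improvement as the patient defines it. Under Standard Drainage in 4.1.2, "The subject must contact the clinical site once he/she has drained <50mL on 3 consecutive drainages performed every other day". The diary in Appendix E says: "Please drain fluid through the catheter every other day using a one liter bottle".

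Dosing depends on the same outcome. Section 4.1.1 states: "Subjects may continue talimogene laherparepvec for up to 9 cycles (i.e. alone or with nivolumab) until resolution of pleural effusion", or until systemic progression.

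**The concern.** In 4.1.2 symptoms can end a drainage or permit an early one, but they never start the one due after the dwell. In 4.1, 4.2 and 5.1.3 breathlessness is what starts it. The two differ for a patient who is comfortable at 24 hours, and such a patient is among the likeliest to be approaching resolution.

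The endpoint is a run of volumes on a set schedule. A comfortable patient who waits for breathlessness may not produce that run, although the effusion may be controlled. A resolution could then be recorded late or missed. Because dosing continues until resolution, the delay could also mean another 4 x 10^8 pfu dose.

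**Working it through.** **The plan's own figure.** The documents give no figure for drainage timing. The design figure in Section 8.2 (45% against 70%, two-sided 0.10, 80% power) does reproduce:

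n = [(1.6449 x sqrt(0.45 x 0.55) + 0.8416 x sqrt(0.70 x 0.30)) / 0.25]^2 = 23.19, rounded up to 24.

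Nothing below changes it.

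**Can the texts be read as one schedule?**

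1. The minimum dwell agrees: at least 24 hours in one text, 24 hours in the other. The difference is the trigger.
2. Section 1.3 lists drainage only as needed as a regimen separate from drainage at set intervals, so these are different regimens.
3. Suppose the symptom wording governs only the first drainage after a dose. Section 4.1.2 starts the every-other-day schedule from that drainage, so the whole series would still wait for symptoms.

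**Timing.** Inputs are a dose on day 0, the next dose on day 14 (day 21 in cycle 1), drainages two days apart and three needed. Let d be the day of the first (post-dwell) drainage. The plan does not say whether that drainage, which follows 200 cc of saline and a 20 cc flush, can count, so both cases are shown. The third drainage may fall on the next dosing day, before instillation.

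- Post-dwell drainage counted: the run is d, d+2, d+4, so d <= interval - 4.
- Not counted: the run is d+2, d+4, d+6, so d <= interval - 6.

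| | Counted | Not counted |
|---|---|---|
| Section 4.1.2 (d = 1): run ends | day 5 | day 7 |
| 14-day cycle: latest d | 14 - 4 = 10 | 14 - 6 = 8 |
| Cycle 1, 21 days: latest d | 21 - 4 = 17 | 21 - 6 = 15 |

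If a drainage on the dosing day is not allowed, the 14-day limits become 13 - 4 = 9 and 13 - 6 = 7. All limits move day for day with the actual dosing interval; visits carry a window of 2 days either way.

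Under 4.1.2 the drainages fall on days 1, 3, 5, 7, 9, 11 and 13, so a 14-day cycle has ample room. Under the symptom wording, a first drainage after day 10 (or day 8) leaves no complete run in that cycle.

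**After the last instillation.** No next dose cuts the run off. Phase II patients may continue nivolumab. Table 6.2 keeps the diary going in those cycles, and the end-of-treatment visit is timed from the last study medication. No general limit applies.

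**Scale only.** Each true resolver finally missed lowers the observed rate by 1/24 = 4.2 percentage points, against a rule of 15 or more out of 24.

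**The case against.** The other side has a good case on strength, less so on substance.

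- **Section 4.1.2 already reads as the governing text.** It is the only section devoted to drainage and says it applies in both phases. The amendment summary records edits explaining drainage there and lists none to the 4.1 schema text, 4.2 or 5.1.3, which fits leftover wording. This stands, and it supports the choice of 4.1.2. It does not remove the contrary instruction from three other sections.
- **A site can comply with 4.1.2 without breaching a prohibition.** This stands. A reader might infer that the two texts cannot both be followed. The only firm limit in 4.1 is no drainage before 24 hours, apart from its allowance for breathlessness. Draining at 24 hours respects it, and 4.1, 4.2 and 5.1.3 speak only of the next drainage, not of later ones. The risk lies with a site or patient who follows the symptom wording.
- **The patient's own instruction is right.** Appendix E asks for every-other-day drainage with no symptom condition. This stands in part, because it mentions neither the dwell nor the first drainage after a dose.
- **Diary review would catch a patient who is not draining.** Day 8 is 7 days after the dose, inside the day 8 and day 10 limits, and Section 6.4.2 requires diary review then. This also stands in part. Day 8 visits exist only in cycles 1 and 2 and may be optional in the expansion.
- **A lost run can be made up** in a later cycle or after the last instillation. This stands. A resolver is missed only if no run is ever completed.

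**Conclusion.** The inconsistency is in the current text and affects how the primary endpoint is collected. It is worth correcting, but it is not a design flaw. The supported conclusion is conditional: if the symptom wording is followed, the qualifying run can start late or not at all in patients whose effusion is controlled, with a delayed or missed resolution and possibly one more dose. Any bias would be downward, since these patients have the least reason to drain. The timing limits rest on the dose-day convention and the two counting cases shown.

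Two stronger inferences are not supported.

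- **A quantified loss of power.** If 5%, 10% or 20% of true resolvers went uncounted, exact power of the 15-of-24 rule at a true 70% would fall from 84.7% to 74.0%, 61.0% or 33.4%. Those shares are assumptions. The documents give none, and the safeguards above make any share hard to guess.
- **A cut-off after the last dose.** For a visit on day 30, limits of 30 - 4 = day 26 or 30 - 6 = day 24 would apply only to a patient who stops both drugs together.

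Appendix D was not available to this review and is not judged.

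**What to change.** Let 4.1.2 govern throughout.

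- In 4.1, 4.2 and 5.1.3, replace the shortness-of-breath clause with: 'after the 24-hour dwell, drain and then continue every other day whether or not short of breath, per Section 4.1.2'.
- Add one line to Appendix E: 'after each study-drug dose wait 24 hours, drain, then drain every other day even without shortness of breath'.
- Leave the early-drainage provisions in 4.1 and 4.1.2 as they are. They differ: 4.1 refers to consultation and to severe shortness of breath, while 4.1.2 refers to dyspnea. This correction should neither merge them nor extend them to 4.2 or 5.1.3.

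The cost is one clause in each of three sections and one diary line. The flush, volume limit, visits, sample size and endpoint definition stay unchanged.

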#### 4.1.1 Cohort Enrollment – Safety Run-in

Since this is the first time talimogene laherparepvec is being given in the intrapleural space (i.e. new route of administration), enrollment in safety run-in cohorts 1 and 2 will be staggered. Each subject will be required to complete the 7-week safety assessment period (i.e. 3 cycles of TVEC including the seroconversion cycle) of dose-limiting toxicity (DLT) before the next subject is enrolled. During the safety run-in period starting in Dose Level 1, patients will only receive intrapleural talimogene laherparepvec. The first dose of talimogene laherparepvec will be administered on Cycle 1, Day 1 at 4ml of  $10^6$  pfu/mL in 200 cc normal saline (intrapleurally) to seroconvert HSV-seronegative patients. Three weeks will be given for seroconversion. Subsequent doses of talimogene laherparepvec at 4ml of  $10^8$  pfu/mL will then be administered IP every two weeks (Q2W) starting on Cycle 2, Day 1 for up to 8 cycles. Patients will be assessed for dose limiting toxicity (DLT) related to IP administration of talimogene laherparepvec after they have completed at least 3 cycles (i.e. 7 weeks) of monotherapy. If  $\geq 2$  patients experience DLT, the study will be discontinued. If 1 patient out of 3 has DLT, 3 additional patients will be recruited and treated at the same dose level. If 0 out of 3 patients or  $\leq 1$  patient out of 6 has a DLT, the study will proceed to Dose Level 2. One week following completion of study therapy, subjects may proceed to systemic therapy per their decision with their physician.

In Dose Level 2 (expected Phase II dose), the first 3 patients will receive both IP talimogene laherparepvec and IV nivolumab. The first dose of talimogene laherparepvec will be administered on Cycle 1, Day 1 at 4mL of  $10^6$  pfu/mL in 200 cc normal saline (IP) to seroconvert HSV-seronegative patients. Three weeks will be given for seroconversion. Subsequent doses of talimogene laherparepvec at 4ml of  $10^8$  pfu/mL + Nivolumab 240 mg IV will be administered every two weeks starting on Cycle 2, Day 1 for up to 8 cycles of therapy. Patients will be assessed for DLTs related to IP administration of talimogene laherparepvec after seroconversion and 2 cycles of combination therapy (i.e., 7 weeks of study treatment). If  $\geq 2$  patients experience DLT, the study will be discontinued. If 1 patient out of 3 has DLT, 3 additional patients will be recruited and treated at the same dose level. If 0 out of 3 or  $\leq 1$  patient out of 6 has a DLT in the dose level 2 cohort, the study will recruit additional patients in Phase II at this dose level and accrue a total of 24 patients as per study goal. All patients treated at dose level 2 in Phase I or Phase II, will be included in analyses of safety and efficacy. Safety stopping rules will ensure the safety of subjects receiving combination treatment in Phase II (see [Statistical Considerations in section 9.0.](#))

Subjects may continue talimogene laherparepvec for up to 9 cycles (i.e. alone or with nivolumab) until resolution of pleural effusion or they experience systemic disease progression. Subjects who have resolution of pleural effusion as defined by

the primary endpoints may continue nivolumab monotherapy per standard of care until disease progression (see section 4.2 for details on treatment and section 6.5.2).

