#### 4.1.4 Safety Assessment Period - Safety run-in:

The safety assessment period for DLT assessment encompasses 3 cycles of study treatment (i.e. 7 weeks total). Three weeks will be given for seroconversion following the first dose of talimogene laherparevec ( $4 \times 10^6$  pfu). Subsequent doses of talimogene laherparevec ( $4 \times 10^8$  pfu) will be given alone or with nivolumab (240 mg IV) every two weeks starting on Cycle 2, Day 1 for up to 8 cycles of therapy. Patients will be assessed for DLTs after seroconversion and 2 cycles of talimogene laherparevec given alone or with nivolumab every 2 weeks. Cohorts will be enrolled according to 3+3 rules and each subject must complete the safety assessment period before the next patient is treated (see above [study schema](#)). If  $\geq 2$  patients experience DLT in a dose cohort, the study will be discontinued.

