## 6.2 Safety Run-in Cohort 2 and expansion (Combination)

Assessments	Pre-Study 	Treatment Period 							Follow up	
		Cycle 1 is 3 weeks in length, subsequent cycles are Q2W							End of TXT 	Long Term FU 
		Cycle 1 Day 1 	Cycle 1 Day 8	Cycle 2 Day 1	Cycle 2 Day 8 	Cycle 3 Day 1	Cycle 4 Day 1	C5 – 9N Day 1		
Informed Consent	X									
HSV-1 antibody	X									
History 	X									
Physical exam 	X	X	X	X	X	X	X	X	X	
Performance Status	X	X	X	X	X	X	X	X	X	
EKG	X						X			
Troponin	X						X			
Chest x-ray	X	As needed and within 21 days of final drainage ≤ 50 mL							X	
Tumor measurement 	X							X 	X 	X
Pregnancy test 	X									
Hematology 	X	X	X	X	X	X	X	X	X	
Serum chemistries 	X	X	X	X	X	X	X	X	X	
Liver function tests 	X	X	X	X	X	X	X	X	X	
Coagulation 	X									
Toxicity Assessment	X	X	X	X	X	X	X	X	X	X
Concomitant Meds	X	X	X	X	X	X	X	X	X	
talimogene laherparepvec IP Q3W 10  PFU		X								
talimogene laherparepvec IP Q2W 10  PFU 				X		X	X	X		
Nivolumab IV Q2W		X		X		X	X	X		
Patient diary 		X	X	X	X	X	X	X	X	

Assesments	Pre-Study 	Treatment Period  Cycle 1 is 3 weeks in length, subsequent cycles are Q2W							Follow up	
		Cycle 1 Day 1 	Cycle 1 Day 8	Cycle 2 Day 1	Cycle 2 Day 8 	Cycle 3 Day 1	Cycle 4 Day 1	C5 – 9N Day 1	End of TXT 	Long Term FU 
Blood/urine/pleura samples to assess viral shedding		X 	X 	X 	X 	X 	X 		X 	
Blood sample for correlative studies 		X		X			X		X	
Tumor biopsy 	X									
Collection of pleural drainage 		X		X			X		X	
Buccal Swab	X 	X 								
Modified Borg 		X		X			X		X	
Survival analysis										X

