## 6.4 Study Treatment Assessments (+/- 2 days)

### 6.4.1 Cycle 1/Day 1 Safety Run-in/Phase II expansion (6.1, 6.2)

Physical examination (including weight and symptom directed medical history  
ECOG Performance Status (see appendix A)

Laboratory evaluations (to be obtained prior to treatment):

- CBC with differential
- Serum chemistries (potassium, sodium, calcium, creatinine, chloride, glucose, magnesium, phosphorus, BUN, albumin, uric acid, and total protein)
- Liver function tests (total bilirubin, direct bilirubin, alkaline phosphatase, AST, ALT)
- Serial sampling of blood/urine/pleura to assess viral shedding (pre-dose & 1hr, 4hr and 6hr post dose samples) following IP talimogene laherparepvec. Pleural fluid will be separated by the LCCC Immune Monitoring and Genomics Facility (IMGF) into two portions: one portion will be used for correlative studies, and the second portion will be distributed to the CTU laboratory for long term storage at -80°C for possible assessment of viral shedding for up to two years after study completion. If insufficient amount of pleural fluid is collected, priority will be given to a sample used for correlative studies.
- Blood samples collected for correlative studies

Concomitant medication(s): All concomitant medications will be recorded.

Toxicity evaluation: Use NCI CTCAE v5.0

Collection of Pleural drainage: prior to talimogene laherparepvec administration, if feasible

For Safety run-in cohort 1 (6.1): Administer premedications, followed by talimogene laherparepvec only  $4 \times 10^6$  pfu via pleurX catheter

For Safety run-in cohort 2 and Phase II expansion (6.2): Administer premedications, followed by talimogene laherparepvec  $4 \times 10^6$  pfu via pleurX catheter + 240 mg nivolumab IV

Modified Borg Scale of Perceived Dyspnea (Provided in 11.6 Appendix F: Borg Scale): Scale ranging from 0 to 10, which evaluates perceived level of shortness of breath.

Patient Catheter drainage diary

Chest x-ray within 21 days of the final drainage of  $\leq 50$  mL, if applicable.

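### Nivolumab has two conflicting start visits (Cycle 1 Day 1 and Cycle 2 Day 1), so exposure in the 7-week DLT window and in Phase II is not defined

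*Combined protocol and SAP*

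**What the plan says.** All of the following is current text in the combined protocol and SAP, not the amendment summary.

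**Start at Cycle 2 Day 1**
- Section 4.1.1, Dose Level 2: the low virus dose is given on Cycle 1 Day 1, three weeks are allowed for seroconversion, and then, with the higher virus dose, "Nivolumab 240 mg IV will be administered every two weeks starting on Cycle 2, Day 1 for up to 8 cycles of therapy". DLTs are judged after the seroconversion cycle plus two cycles of the combination.
- Section 4.1.4 repeats the same start visit and the same limit of 8 cycles for the later virus doses, with or without nivolumab.

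**Start at Cycle 1 Day 1**
- Section 6.4.1, the Cycle 1 Day 1 visit: the order opens with "For Safety run-in cohort 2 and Phase II expansion (6.2): Administer premedications, followed by talimogene laherparepvec". It names the 4 x 10^6 dose and closes with "pfu via pleurX catheter + 240 mg nivolumab IV".
- Section 6.2 table: the row "Nivolumab IV Q2W" is marked at Cycle 1 Day 1, in the same column as the seroconversion dose, and again at Day 1 of every later cycle.

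**Unclear**
- Section 4.1 has nivolumab given with the 10^8 pfu/mL virus dose "for up to 9 cycles in the Dose Level 2 cohort, with 3 week interval between cycle 1 and cycle 2 to allow for seroconversion". The Section 4.2 table provides for only 8 doses at that strength.
- The text of Section 4.2 calls for an "infusion on D1 of each cycle every two weeks", although Cycle 1 lasts three weeks. The Section 4.2 table starts nivolumab on a Day 1 without naming the cycle.

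**The concern.** On Cycle 1 Day 1 a Dose Level 2 patient either receives a nivolumab infusion or does not, and the protocol orders both. Four things rest on the answer.

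1. **The decision to open Phase II.** The 3+3 rule at Dose Level 2 counts DLTs over a window that Section 4.1.1 describes as one seroconversion cycle and two combination cycles. If nivolumab starts at Cycle 1, the seroconversion cycle is itself combination treatment and that description no longer fits.
2. **Which events count as DLTs.** Section 4.1.3 does not count reactions attributed to nivolumab alone that would be expected in standard use, and it replaces the patient. In days 1 to 21 that exemption can apply under one reading and cannot under the other. Section 8.2 carries the DLT exceptions into the Phase II toxicity boundary.
3. **The three-week correlative sample.** Blood and pleural fluid at Cycle 2 Day 1 are taken before that day's treatment (Section 6.4.3). They follow virus alone under one reading and the combination under the other, whereas the hypothesis in Section 1.8 is about the combination.
4. **Pooling.** Sections 4.1.1 and 8.1 put every Dose Level 2 patient, run-in or Phase II, into one safety and efficacy analysis. If start days were mixed, the mix would enter the primary analysis of 24.

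**Working it through.** **Inputs**
- Cycle 1 lasts 21 days and later cycles 14 days (Section 6.2, footnote 2).
- Nivolumab is 240 mg per infusion (Section 4.2).
- The DLT period ends 14 days after the third virus dose and is stated as 7 weeks (Section 4.1.3).
- Virus is given through Cycle 9 (Section 6.2, footnote 9).

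**The plan's own figure.** The first three virus doses fall on days 1, 1 + 21 = 22, and 22 + 14 = 36. The window ends on day 36 + 14 = 50, and (50 - 1)/7 = 7.0 weeks. The stated window reproduces and is the same under either start day.

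**Nivolumab inside the window**, counting doses before day 50:

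| | Start Cycle 2 Day 1 (4.1.1, 4.1.4) | Start Cycle 1 Day 1 (6.2, 6.4.1) |
|---|---|---|
| Dose days | 22, 36 | 1, 22, 36 |
| Doses | 2 | 3 |
| Cumulative amount | 2 x 240 = 480 mg | 3 x 240 = 720 mg |
| First dose to end of window | 50 - 22 = 28 days | 50 - 1 = 49 days |
| Doses before the Cycle 2 Day 1 sample | 0 | 1 |
| Doses through Cycle 9 Day 1 | 8 (1,920 mg) | 9 (2,160 mg) |

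The difference in the window is (720 - 480)/480 = 50%. First exposure differs by 22 - 1 = 21 days.

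**A third reading.** Taking the 14-day interval literally from Cycle 1 Day 1 gives days 1, 15, 29 and 43: 4 doses, 960 mg. The Section 6.2 table has no day-15 visit, so this schedule cannot be run as the visits stand.

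**Sensitivity.** The window of plus or minus 2 days on visits could bring the Cycle 4 Day 1 infusion just inside the DLT window. That adds one dose to both columns and leaves the one-dose gap.

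**What does not move.** The Section 8.2 calculation does not involve the start day. With null 0.45, alternative 0.70, two-sided alpha 0.10 and n = 24, approximate power is Phi[(0.25 - 1.645 x sqrt(0.45 x 0.55/24)) / sqrt(0.70 x 0.30/24)] = 81.2%, against 80% stated.

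**The case against.** The conflict between Sections 4.1.1 and 4.1.4 on one side and Sections 6.2 and 6.4.1 on the other cannot be put down to the PDF extraction: the prose of 6.4.1 says in words what the table marks. The arguments on the other side concern how much follows from it.

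- **The DLT rule is aimed at the virus.** Section 4.1.1 assesses DLTs related to the intrapleural virus, and Section 4.1.3 exempts expected reactions to nivolumab alone. The start day therefore acts mainly through events not attributed to nivolumab alone. This limits the effect on the DLT count but does not remove it. The exemption itself depends on whether nivolumab has been given, and combined toxicity is what the Dose Level 2 run-in is there to detect.
- **Nivolumab has no fixed ceiling.** It may continue until progression, so 8 against 9 doses does not describe competing caps. This stands. Those totals apply only to the co-administration phase through Cycle 9. The 2 against 3 in the DLT window does not depend on them.
- **It is not a different dose level.** Each infusion is 240 mg either way, and the 50% is a cumulative count on a base of two infusions. That is correct, and the figure should be read that way.
- **Some of the texts are not clean evidence.** Sections 4.1 and 4.2 are internally mixed and support neither start day firmly. That also stands: they add ambiguity, while the firm contradiction is between the two pairs of sections.
- **Harm from pooling is hypothetical and the correlative aims are exploratory.** Nothing in the documents shows that patients were treated differently, run-in enrolment is one patient at a time, and data are entered by one centre. Section 1.8.2 also lists total dose received as a candidate predictor. These points lower the likelihood and weight of the harm. They do not tell the team what to give on day 1.

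**Conclusion.** The concern holds. The protocol gives contradictory orders for nivolumab on the first treatment day of every Dose Level 2 and Phase II patient, and nothing sets precedence. Exposure inside the 7-week DLT window is 2 doses (480 mg) or 3 (720 mg), with 28 or 49 days from first nivolumab to the end of the window. Through Cycle 9 the virus is accompanied by 8 or 9 nivolumab doses.

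The undefined part is nivolumab in Cycle 1 and the resulting dose counts. The virus schedule, the window length, the rejection rule and the sample size are consistent on this point. The counts assume nominal visit days and no missed or delayed doses. Whether any patients were treated under different readings cannot be known from the documents.

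This must be fixed because a treatment instruction is contradictory as written and the step from run-in to Phase II relies on it. No view is taken on which start day is right.

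**What to change.** - Reconcile Sections 4.1, 4.1.1, 4.1.4, 4.2, 6.2 and 6.4.1 to one nivolumab start visit and one maximum number of cycles given together with the virus, stated separately from continuation of nivolumab until progression.
- In Section 4.2, make the dosing interval agree with the three-week first cycle.
- In Sections 4.1.1, 4.1.3 and 4.1.4, state how many nivolumab doses fall inside the DLT window and whether the seroconversion cycle counts as combination treatment.
- In Section 1.8, state whether the Cycle 2 Day 1 sample represents virus alone or the combination.
- Record the actual start visit for any Dose Level 2 patient already treated. If start visits differ, report this with the DLT assessment and with the pooled analysis.

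The cost is amendment wording, with no extra patients or procedures. Under Section 9.6 the amendment needs IRB approval and goes to Amgen for review, and a revised consent form might be required if the change substantially alters the design or the risk to patients.
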